# Secondary Endpoints

- For mTOR inhibitor patients, oral mucositis grade will be assessed at the following times: baseline, weekly during Cycle 1, and Day 1 of Cycle 2 and beyond, and end of study. For esophagus radiation patients, esophagitis grade will be assessed at the following times: baseline, weekly during radiation, end of treatment (or final week of radiation treatment based on number of weeks of radiation), and 1 month and 6 months post radiation therapy.
- For mTOR inhibitor patients, QOL will be assessed by MDASI-HN at the following times: baseline, Day 15 of Cycle 1, Day 1 of Cycles 2 and beyond, end of study, and 3 months and 6 months post end of treatment. For esophagus radiation patients, QOL will be assessed by MDASI-HN at the following times: baseline, Weeks 3, 5, and 7 of radiation, end of treatment (or final week of radiation treatment based on number of weeks of radiation), 1 month, 3 months, and 6 months post radiation therapy. For mTOR inhibitor patients, Patient Satisfaction with Study Medication will be assessed at Day 1 of Cycles 2 and beyond. For esophagus radiation patients, Patient Satisfaction with Study Medication will be assessed at Weeks 3, 5, and 7, end of treatment (or final week of radiation treatment based on number of weeks of radiation treatment based on number set as a Day 1 of Cycles 2 and beyond. For esophagus radiation patients, Patient Satisfaction with Study Medication will be assessed at Weeks 3, 5, and 7, end of treatment (or final week of radiation treatment based on number of weeks of radiation), and 1 month post radiation therapy.
- For mTOR inhibitor patients, body weight will be assessed at the following times baseline, weekly during Cycle 1, and Day 1 of Cycle 2 and beyond, and end of study. For esophagus radiation patients, body weight will be assessed at the following times: baseline, weekly during radiation, 1 month and 6 months post radiation therapy.
- For esophagus radiation patients, muscle breakdown will be assessed at baseline, weekly during radiation, 1 month and 6 months post radiation therapy.

## 12.3 Sample Size

There will be a total of 180 patients in this study. The cohort of patients on mTORbased regimens will be 100, and the cohort of patients on radiation regimen will be 80.

For esophagus radiation, published data indicate that the distribution of patients by esophagitis grade is 0-1: 26%, 2: 37%, 3: 37% for patients not given glutamine. If we target a modest treatment effect (0-1: 50%, 2: 38%, 3: 12%) then 40 patients per treatment arm would give us 81% power (assuming a two-sided 5% alpha and use of the Wilcoxon rank sum test for analysis).

For mTOR inhibitor patients, we have unpublished data from 87 patients indicating that the distribution of patients by oral mucositis grade is 0-1: 69%, 2: 22%, 3: 9% for patients not given glutamine. If we target (0-1: 95%, 2: 5%, 3: 0%) as the results in the glutamine arm, then 50 patients per arm would give us 94% power (assuming a two-sided 5% alpha, and use of the Wilcoxon rank sum test for analysis).

These calculations were made using nQuery Advisor 7.0.

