### 12.4 Statistical Analysis Plan

Note: Analyses will be performed separately for patients treated with mTOR inhibitors and patients with esophagus radiation.

For the primary objective, we will use the Wilcoxon rank sum test to compare the ordered categories of mucositis/esophagitis severity between treatment arms. A patient must complete at least 60% of the planned doses of placebo or glutamine to be considered evaluable in the statistical analysis. As a sensitivity analysis for the appropriateness of 60% dosing cut-off, we will analyze the outcome according to the proportion of drug taken. The proportional of drug taken will be computed as the ratio of number of doses taken to the total number of doses prescribed. For the mTOR inhibitor group, the denominator will reflect the total time that each patient is on the study. For the esophagus radiation group, the denominator will reflect the total number of doses that are prescribed during the delivery of radiation.

For the secondary objectives/endpoints, we will compare between treatment arms (1) the trajectories of the mucositis/esophagitis scores over time using linear mixed effects; (2) the proportion of patients developing mucositis/esophagitis using a Pearson chi-squared test; (3) the proportion of patients developing grade 3 or higher mucositis/esophagitis using a Pearson chi-squared test; (4) the duration of mucositis/esophagitis using the Wilcoxon rank sum test; (5) the time to develop mucositis/esophagitis using Kaplan-Meier estimates and the log rank test (due to right censoring in patients not developing mucositis/esophagitis); (6) the proportion of patients having treatment interruptions using a Pearson chi-squared test; (7) the

weight change using the Wilcoxon rank sum test; and (8) the QOL survey scores using the Wilcoxon rank sum test.

For the secondary objective of describing the toxicity profile, descriptive statistics will be provided on the grade and type of toxicity by treatment arm.

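### The 81% and 94% power figures hold only if every enrolled patient is evaluable; the 60%-dose rule has no allowance in the sample size, and the radiation cohort has no margin

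*Combined protocol and SAP*

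**What the plan says.** Section 12.3 (Sample Size) opens with "There will be a total of 180 patients in this study" and splits them into 100 on mTOR-based regimens and 80 on radiation. Section 5.0 gives the same cohort sizes as the numbers to be enrolled, and section 12.5 randomises equally within each cohort.

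For radiation, section 12.3 assumes "0-1: 26%, 2: 37%, 3: 37% for patients not given glutamine" against 50%, 38% and 12% with glutamine, and states that 40 "patients per treatment arm would give us 81% power". For mTOR it assumes "0-1: 69%, 2: 22%, 3: 9% for patients not given glutamine" against 95%, 5% and 0%, and states 94% power with 50 per arm. The basis in each cohort is a two-sided 5% Wilcoxon rank sum test, and section 12.4 names the same test for the primary analysis, run separately in each cohort.

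Section 12.4 then adds: "A patient must complete at least 60% of the planned doses of placebo or glutamine to be considered evaluable in the statistical analysis". A sensitivity analysis by proportion of drug taken is planned. The protocol text contains no expected non-evaluable or dropout rate, no inflation of enrolment, no replacement of non-evaluable patients and no primary analysis of all randomised patients.

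**The concern.** Enrolment of 80 and 100 is exactly 2 × 40 and 2 × 50. The power figures therefore need every enrolled patient to reach the analysis, while the analysis section has a rule that takes patients out of it.

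The protocol does foresee some loss. Section 8.0 lists withdrawal of consent and refusal of study medication, section 10.2 requires evaluability data for every registrant, and section 12.4 plans to examine the 60% cut-off. In the radiation cohort the suspension has to be swallowed (section 3.2) twice a day (section 5.1), and esophagitis of grade 2 or 3 is graded by altered swallowing (section 9.0). Section 12.3 expects those grades in 37% + 37% = 74% of controls.

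At stake is how a non-significant radiation result is read. That cohort is analysed alone, so the mTOR cohort lends it no power. By simulation, the chance of missing the targeted effect is 19% at the stated power, 23% with 10% of patients lost and 28% with 20% lost.

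**Working it through.** **Inputs.** From section 12.3: the grade distributions (0-1 / 2 / 3), radiation 26/37/37 against 50/38/12 and mTOR 69/22/9 against 95/5/0; n = 40 and 50 per arm; two-sided alpha 0.05; Wilcoxon rank sum test. Assumed here, because the documents give no figure: a non-evaluable rate of 5% to 30%, equal in both arms, with the targeted effect unchanged among evaluable patients.

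**Step 1: effect size.** θ = P(control grade worse) + ½ P(tie).

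- Radiation: worse = 0.37 × 0.50 + 0.37 × 0.88 = 0.5106. Ties = 0.26 × 0.50 + 0.37 × 0.38 + 0.37 × 0.12 = 0.3150. θ = 0.5106 + 0.1575 = 0.6681.
- mTOR: worse = 0.22 × 0.95 + 0.09 × 1 = 0.2990. Ties = 0.69 × 0.95 + 0.22 × 0.05 = 0.6665. θ = 0.2990 + 0.33325 = 0.63225.

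**Step 2: reproduce the plan's figures.** Normal approximation to the Mann-Whitney statistic:

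power = Φ{[n²(θ − 0.5) − 1.96·SD0] / SD1}

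- SD0² = (n²/12)·[(2n + 1) − Σ(t³ − t)/(2n(2n − 1))], the tie-corrected null variance, where t is the expected number of patients in each category over both arms.
- SD1² = n²·[(n − 1)(a + b) + c], the variance under the alternative. Here a and b are the variances of the expected pairwise score (1 worse, ½ tie, 0 otherwise) over control and over glutamine patients, and c is the variance of a single pairwise score. Radiation: a = 0.0730, b = 0.0532, c = 0.1430. mTOR: 0.0551, 0.0098, 0.0659.

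Radiation, n = 40: (268.96 − 1.96 × 97.37)/90.03 = 0.868, so power is 80.7% (stated 81%).

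mTOR, n = 50: (330.63 − 1.96 × 96.89)/90.09 = 1.562, so power is 94.1% (stated 94%).

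Simulating the tie-corrected test (100,000 trials per setting) gives 81.0% for radiation and 96.0% for mTOR. The two methods agree for radiation. For mTOR they differ by about two points, and the normal approximation is the one that matches the protocol.

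**Step 3: apply the evaluability rule.** Replace n by the evaluable number per arm.

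| Radiation, non-evaluable | n per arm | Normal approx. | Simulation |
|---|---|---|---|
| 0% | 40 | 80.7% | 81.0% |
| 5% | 38 | 78.6% | 78.9% |
| 10% | 36 | 76.2% | 76.8% |
| 20% | 32 | 70.8% | 71.7% |
| 30% | 28 | 64.6% | 65.7% |

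| mTOR, non-evaluable | n per arm | Normal approx. | Simulation |
|---|---|---|---|
| 0% | 50 | 94.1% | 96.0% |
| 10% | 45 | 91.5% | 94.0% |
| 20% | 40 | 87.9% | 91.1% |
| 30% | 35 | 83.1% | 87.4% |

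On the normal approximation, mTOR power is 80.7% at 33 per arm, a loss of 17/50 = 34%.

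**Step 4: if all randomised patients were analysed instead.** The number per arm stays at 40 or 50. Suppose a fraction f of the glutamine arm has the placebo distribution, so that the arm follows f × placebo + (1 − f) × glutamine. For radiation this gives 47.6/37.9/14.5 at f = 10% and 45.2/37.8/17.0 at f = 20%. Simulated power is 72% and 61% for radiation, and 88% and 76% for mTOR. Non-adherent patients are given no benefit at all here, so these figures are a bound.

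**The case against.** The strongest reply is that section 12.3 makes a conditional statement, 40 analysed patients per arm give 81%, and that this statement is right. That stands. A reader might infer that the sample size was miscalculated, or that the radiation cohort simply does not have its stated power. The documents support neither: the arithmetic reproduces, and with no exclusions 81% holds.

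Some features may also keep radiation losses small. The dose denominator counts only doses prescribed during radiation (section 12.4), not the four weeks afterwards. The endpoint is the highest grade by week six (section 12.2), grading is weekly, and section 5.2 allows it by phone, so one missed visit need not cost a patient. These points count against giving 20% or 30% loss the same weight as 10%. They do not make the loss zero.

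Three other stronger readings should be resisted. The simulated mTOR values start at 96%, so setting them beside the stated 94% misleads. The figures in step 4 are not the expected power of this plan, which contains no such primary analysis, and a patient who takes half the doses may still benefit. And nothing in the documents says that a null result would be taken as proof of no effect; that is a risk, not a stated intention.

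Reading 40 and 50 as evaluable numbers does not rescue the text, since enrolment would then have to exceed 80 and 100. The planned sensitivity analysis tests the cut-off and restores no power.

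**Conclusion.** The point holds as a missing condition, not as a calculation error. Power for 40 and 50 analysed patients per arm is attached to cohorts of exactly 80 and 100 enrolled, and the plan's own evaluability rule can only reduce the number analysed. On the scale that reproduces each stated figure, any exclusion puts power below it.

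The radiation cohort is the main concern because it has no margin: 79%, 77%, 72% and 66% at 5%, 10%, 20% and 30% loss, by simulation. The documents set no 80% target, but by that common yardstick two patients lost per arm are enough to fall short. The mTOR cohort also drops (about 91.5%, 88% and 83% at 10%, 20% and 30%) yet stays above 80% until about one third are lost.

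The sizes rest on assumed rates, equal loss in both arms and an unchanged effect among evaluable patients. If exclusion is related to the outcome, the comparison may also be biased; that is a separate question, which these figures do not address.

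**What to change.** Keep 80 and 100 patients. In section 12.3:

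1. State that 81% and 94% apply only if all enrolled patients are evaluable.
2. Give a justified expected evaluable number per arm and the power at that number. With 90% evaluable, for example, it is 36 and 45 per arm.
3. Add a short table for 90%, 80% and 70% evaluable, using one calculation method for both cohorts. The normal approximation reproduces both stated figures: radiation 76%, 71%, 65%; mTOR 91.5%, 88%, 83%.
4. If a primary analysis of all randomised patients is adopted, report the diluted-effect power instead, labelled as a bound that assumes no benefit in non-adherent patients (radiation 72% or 61%, mTOR 88% or 76%, by simulation at 10% or 20% non-adherence; recompute if another method is chosen).

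The cost is a few sentences, one small table and a less favourable stated power. No extra patients are needed.

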# 2.2 Rationale

# 2.2.1 Rationale in mTOR Treatment Patients

Anti-cancer agents damage cells in the intestine and oropharynx, which leads to mucositis. Mucositis induced by anti-cancer treatment may be the result of multiple factors. Anti-cancer agents inhibit the DNA synthesis of rapidly proliferating cells in the mucosa, and it hinders the renewal capacity of basal epithelium. Subsequently, that results in mucosal atrophy and collagen breakdown thus leading to ulceration.

Mucositis is a notable side effect and dose-limiting toxicity for patients in mTORbased regimens. Mucositis is further associated with dehydration and weight loss among patients undergoing temsirolimus-based trials. In a recent study, mucositis was noted to be the most frequent adverse event overall (73.4%) among 2,822 patients who received a temsirolimus-based, everolimus-based, or ridaforolimusbased regimens. In a study of single-agent temsirolimus treatment in patients with advanced renal cell carcinoma, mucositis was 41.3%.

In a recent data review, we assessed the incidence and severity of mucositis in 87 patients who received one of 3 temsirolimus-based combination trials. Overall, the incidence of any grade of mucositis in our temsirolimus-based combination trials was 64.4%. The incidence rate of mucositis greater than grade 2 was higher at 9.2%. We also examined the effectiveness of our mucositis management, which included one or more of the following: xyloxylin (1:1:1 ratio of diphenhydramine, Maalox, lidocaine; 10 milliliters (mL) swish/ swallow every 6 hours as needed), Caphosol (sodium phosphate; 15 mL swish/spit every 4 hours as needed), valacyclovir (500 mg *per os* 3 times daily), Biotene mouth wash (every 4 hours as needed), and Carafate (1 gram (gm)/ 10 mL; 10 mL swish/swallow or spit every 6 hours as needed) as previously described by Naing *et al.*, 2011. However, there was no standard protocol to treat mucositis. Based on physician discretion, there were some patients who received one or more of our mucositis regimens.

A better regimen for mucositis is indeed warranted. Although not utilized in our 3 trials, oral glutamine may be a promising regimen for mucositis treatment. Use of oral glutamine during and after the anti-cancer treatment has been shown to reduce the duration and severity of mucositis.

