# 12.2 Study Endpoints

# **Primary Endpoints**

• For mTOR inhibitor patients, the severity of oral mucositis will be taken as the maximum grade observed during the 6-month study period. For esophagus radiation patients, the severity of esophagitis will be taken as the highest grade observed by week six.

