## **Stopping Rules**

We will perform semi-annual futility analyses using Bayesian predictive probability methods. These analyses would be timed to occur at the time of our annual DSMB review as well as mid-way in between the meetings. The more frequent interim futility analysis will allow us to determine in a more timely fashion when and if there is sufficient evidence that it is unlikely that we would conclude that one treatment was better than the other if we completed planned enrollment. Consideration should be given to stopping the trial early for futility if the predicted probability that a significant difference between glutamine and placebo would be observed in the trial if it were continued to completion is < 5%.

Separate analyses will be performed for the mTOR inhibitor patients and for the esophagus radiation patients.

The study statisticians will conduct the analyses and send the results to the DSMB for consideration. The PI will not be notified of the results of these analyses unless the DSMB determines to recommend that study enrollment be stopped.

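### Does leaving the Wilcoxon severity categories unlisted undermine the 94% power stated for the mTOR cohort?

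*Combined protocol and SAP*

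**What the plan says.** Section 12.3 states the control assumption for the mTOR cohort as the "distribution of patients by oral mucositis grade is 0-1: 69%, 2: 22%, 3: 9% for patients not given glutamine". The alternative reads "If we target (0-1: 95%, 2: 5%, 3: 0%) as the results in the glutamine arm". With 50 per arm, a two-sided 5% level and the Wilcoxon rank sum test, it reports 94% power. The radiation cohort is treated the same way: 26/37/37% against 50/38/12% in groups 0-1, 2 and 3, with 40 per arm and 81% power.

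Section 12.2 (Primary Endpoints) says that "the severity of oral mucositis will be taken as the maximum grade observed during the 6-month study period". Section 12.4 says "we will use the Wilcoxon rank sum test to compare the ordered categories of mucositis/esophagitis severity between treatment arms", and does not list the categories. Among the secondary analyses it compares "the proportion of patients developing mucositis/esophagitis using a Pearson chi-squared test", which does separate grade 0 from grade 1.

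Section 2.2.1 describes a review of 87 patients: "the incidence of any grade of mucositis in our temsirolimus-based combination trials was 64.4" per cent, and "The incidence rate of mucositis greater than grade 2 was higher at 9.2" per cent.

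**The concern.** The power figure and the endpoint can be read as using different scales. In section 12.3, grades 0 and 1 are tied. In section 12.2 the outcome is a maximum grade, and section 9.0 grades by CTCAE, where grade 1 stands on its own. An analyst who ranks each grade separately splits a cell holding 69% of controls, and the glutamine target does not say how its 95% divides between grades 0 and 1. On that reading the 94% is not the power of the test performed, and no other figure can be put in its place.

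More than labelling would be at stake. The same data could be significant on one scale and not on the other, so an unstated choice could settle the primary result. The futility rule under Stopping Rules uses "the predicted probability that a significant difference between glutamine and placebo would be observed in the trial if it were continued to completion", so it depends on the same choice.

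**Working it through.** **Formula.** Let θ be the chance that a glutamine patient has a lower grade than a control patient, counting ties as one half. With n per arm and p̄ the average of the two arms' cell shares:

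- SE₀ = √[(1 − Σp̄³)/(6n)], the tie-corrected null standard error.
- SE₁ = √[(s_T + s_C)/n], where s_T and s_C are the variances, over glutamine and control patients, of each patient's average score against the other arm.
- Power = Φ[(θ − 0.5 − 1.96·SE₀)/SE₁].

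**The plan's own figures (section 12.3 inputs).** mTOR, pooled, n = 50:

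- θ = 0.95(0.345 + 0.22 + 0.09) + 0.05(0.11 + 0.09) = 0.6223 + 0.0100 = 0.6323.
- p̄ = 0.82, 0.135, 0.045, so Σp̄³ = 0.5539 and SE₀ = √(0.4461/300) = 0.0386.
- s_T = 0.0098 and s_C = 0.0551, so SE₁ = √(0.0649/50) = 0.0360.
- Power = Φ[(0.1323 − 0.0756)/0.0360] = Φ(1.57) = 94.2%.

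Simulating the tie-corrected test gives 96.1%. The same formula for radiation (n = 40, θ = 0.6681) gives 81.1%, and simulation 81.2%. Both stated figures stand.

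**Control split between grades 0 and 1.** Take the 87 patients of section 2.2.1 and the 87 of section 12.3 as one series. The documents do not say so, but the size and the 9.2% and 9% agree. Then 56/87 = 64.4% any grade, 60/87 = 69.0% grade 0-1, 19/87 = 21.8% grade 2 and 8/87 = 9.2% above grade 2. The only whole numbers that fit are 31, 29, 19 and 8 at grades 0, 1, 2 and 3 or higher, so control grade 0 is 31/87 = 35.6%.

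**Four grades ranked separately.** Control 35.6/33.4/22/9; glutamine g/(95 − g)/5/0; n = 50.

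| Glutamine grade 0 (g) | What it implies | θ | SE₀ | SE₁ | Formula | Simulation |
|---|---|---|---|---|---|---|
| 35.6% | no mucositis prevented outright | 0.586 | 0.0533 | 0.0536 | 36.5% | 36.9% |
| 49% | control 0:1 ratio kept (0.95 × 35.6/69) | 0.632 | 0.0535 | 0.0514 | 70.2% | 70.6% |
| 62% | the 26-point gain all goes to grade 0 | 0.677 | 0.0531 | 0.0487 | 93.3% | 93.0% |
| 70% | some grade 1 also prevented | 0.705 | 0.0525 | 0.0467 | 98.5% | 98.3% |

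A common odds ratio would be (0.95/0.05)/(0.69/0.31) = 19/2.226 = 8.54. Applied to the control grade 0 odds of 0.356/0.644 = 0.553, it gives 4.72, a grade 0 share of 4.72/5.72 = 83%, with power over 99%.

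The 49% row shows the mechanism: θ is almost the pooled value, but splitting the large tied cell raises SE₀ from 0.0386 to 0.0535.

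**Radiation.** The control grade 0 share is not given. Assuming it is 10% to 75% of the 0-1 cell, separate ranking gives 79-80% at a constant ratio, 65-79% if grade 0 is unchanged, and 84-91% if every prevented case becomes grade 0.

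**The case for a change.** The best case for acting is that the choice is open and can matter. Nothing in sections 12.2 or 12.4 says that grades 0 and 1 are combined. Applied to the same simulated mTOR trials, the two readings disagree on significance in 60% of trials if glutamine leaves grade 0 at 36%, in 26% if the 0:1 ratio holds, and in 7% if all prevented cases become grade 0. The statistician has access to the assignments (Unblinding Procedure) and the study statisticians run semi-annual analyses, so a scale left unwritten could be chosen after seeing data. One sentence would close the gap.

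The arithmetic stands, and so does the observation that the pooling is inferred. Three things weaken the conclusion. First, the scale is not undocumented: section 12.3 sets out groups for both cohorts and ties them to the Wilcoxon test before any data, so a departure from them would be visible. Section 12.2 defines how a patient's severity is derived, not how many ranks there are. Second, the low power figures need an odd pattern. At 37%, glutamine cuts grade 2 or higher from 31% to 5% yet prevents no mucositis, so grade 1 rises from 33% to 59%. Third, pooling is not plainly the better scale to impose. It gives up the grade 0 versus 1 contrast in the primary test, and the secondary any-mucositis chi-squared test recovers it only partly: about 27% power if grade 0 rises from 36% to 49%, and 79% if it rises to 63%.

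The futility point adds nothing separate. That rule uses whatever the primary test is, and crossing its threshold only calls for consideration of stopping.

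**Conclusion.** The plan needs no change. The 94% and 81% are right for the categories section 12.3 states, and section 12.4 reads naturally as testing those same categories. On that reading the endpoint, test and sample size agree. On the other, the tie-corrected Wilcoxon test is still valid at 5%, and mTOR power could be below or above 94%: about 71% at a constant 0:1 ratio, 93% if prevented cases become grade 0, over 99% under a common odds ratio, and 37% only in the extreme case. No passage gives the split that would choose among these, so they do not show the stated power to be wrong.

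What is left is an unwritten detail that an analyst would fill from section 12.3, and beyond that a choice between two defensible scales, each with a cost. Writing the categories down would be harmless, but it would alter neither the sample size nor the stated power. The four-grade figures assume that the two descriptions of 87 patients are one series, that the section 12.3 target holds, and that 50 patients per arm are analysed. The radiation ranges also rest on an assumed control grade 0 share.
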